Members of the study team have verified the accuracy of this method of identifying cesarean section during the second stage of labor by cross-checking a Clarity pull of EMR data with chart audit for a random sample of 10 patients.

Medical staff inclusion criteria: all 120 staff members (staff physicians, residents, nurses, surgical technicians) at Regions hospital who practice in the Birth center who underwent required simulation education regarding delivery of deeply impacted fetal heads during second stage cesarean section (50 physicians and 65 nurses and 5 techs) and completed the surveys as part of the QI simulation project.

ii. Sample size

Patients: A data pull conducted by an HP Institute RIIS programmer in September 2017 indicated that there are 80 patients per year at Regions hospital having second stage cesarean sections and 80 patients per year at Methodist hospital having second stage cesarean sections. This study will gather data via programming and chart audit on the following counts of patients in these time period:

- A. July 1, 2014 – June 30, 2015 (80 Regions patients)
- B. July 1, 2015 – June 30, 2016 (80 Regions patients)
- C. July 1, 2016 – December 31, 2017 (120 Regions, 120 Methodist) - 18 mo PRE period
- D. January 1, 2018 – June 30, 2019 (120 Regions, 120 Methodist) - 18 mo POST period

Different subsets of patients will be used for different research questions. For research questions 1.1, 1.2, 2.2 Group C above will serve as the pre-period patients and Group D for post-period patients. Thus, the total patient sample size for these research question is expected to be n=480. For research question 2.3, in addition to Groups C and D, we will also include utilize the 160 patients from Regions in Groups A and B for a sample size of 400 at Regions and 240 at Methodist (n=640 total).

Medical staff sample size: The simulation center staff will survey 120 staff (50 physicians, 65 nurses, and 5 techs) immediately before and after the required simulation education as part of an existing QI project. This QI project data will be used to address

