research question 2.1. The simulation center and medical staff will also contact staff for a survey 6 months following the simulation for the QI project. With an expected response rate to the first and second surveys of 100% (because staff are surveyed at the simulation event), we will have n=120 complete first and second surveys. The response rate for the 6 month survey is expected to be 80%, yielding 96 surveys for this time period.

c. Data collection process

i. Data sources: Data sources for this study are: 1. Data pull from HP electronic medical record; 2. chart review; and 3. medical staff surveys from the simulation QI project.

Patient sample: A Clarity pull of EMR data by the Institute RIIS programmer will gather many of the needed data elements. For data elements not readily available with a programmatic data pull, two University of Minnesota medical students along with [name] will conduct manual chart reviews of 640 patients to obtain the needed data elements (see outcomes table below).

Staff sample: Staff-provided information from the simulation QI project. Pre and post electronic surveys of medical staff at the time of the simulation event as well as email surveys 6 months after the simulation event. Surveys will be administered using REDCap. These data collection activities are being done for a QI project, but this QI project data will be used to address research question 2.1

ii. Process steps for identification of patients or records:

Patient data: The study programmer (HP Institute RIIS programmer) will use the inclusion criteria specified earlier and used for the preliminary data counts to gather patient data on the expected 640 patients who are expected to be study-eligible at Regions and Methodist Hospitals in the pre and post-simulation periods. The data pull for patient identification will occur at multiple times to accommodate data needs for specific research questions. A chart review (described below) will be conducted to gather additional morbidity data.

iii. Process steps for data acquisition

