Staff survey: The pre and post staff surveys are used for the QI project to assess staff perceptions of the required simulation training, and are included as the end of the narrative as appendices. These surveys use items developed for this project rather than existing tools. Surveys include a label to identify whether they are gathered before or after the simulation, and contain items such as confidence in handling second stage cesarean sections.

f) Statistical analysis plan

Descriptives (mean, standard deviation, proportion) and frequency distributions of all variables will be computed and examined for distribution shape, outliers, missing data, and implausible data. Tables of descriptive statistics summarizing patients in both care systems (Regions, Methodist)

will be created. Because there are only 2 primary outcomes (both of which are composite variables), there will be no control for multiple testing. Inferential analysis of secondary endpoints will be considered exploratory with the known limitation that multiple testing could yield type 1 errors. Covariates in regression analysis will be specified a-priori on the basis of theory and when such covariates are unbalanced in comparison groups.

Research question 1.1: Does the simulation protocol decrease a composite variable of maternal morbidity defined as a) extension of uterine incision, b) operative blood loss > 1000 mL, c) requirement of transfusion, d) wound infection within 6 weeks, and d) endometritis within 6 weeks, at Regions Hospital compared to morbidity over the same time period at Methodist Hospital?

Analytic sample: 480 maternal patients (120 Regions before/120 after simulation; 120 Methodist before/120 after simulation). Each sample of 120 is viewed as an independent sample.

Analytic approach: Logistic regression will be used to predict the composite maternal morbidity endpoint (0/1) from hospital (Regions, Methodist), time (pre or post simulation), and their interaction. Covariates will be included if needed as described earlier. Model-based proportions, standard errors, and 95% CIs for each hospital for each time point, change over time, and differential change over time by hospital will be computed. A significant hospital * time interaction and pattern of effects showing more improvement over time in Regions than Methodist will support the underlying hypothesis of differential improvement over time favoring Regions and potentially due to the effects of the simulation.

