Research question 1.2: Does the simulation protocol decrease a composite variable of infant morbidity defined as a) 5 minute APGARs <7, b) NICU admission, c) umbilical cord arterial pH <7.1, and d) fetal injury, at Regions Hospital compared to morbidity over the same time period at Methodist Hospital?

Analytic sample: 480 infant patients (120 Regions before/120 after simulation; 120 Methodist before/120 after simulation). Each sample of 120 is viewed as an independent sample.

Analytic approach: Same as 1.1, but uses the endpoint of composite infant morbidity

Research question 2.1: Does Regions hospital provider and team confidence regarding delivery of impacted fetal head increase after participating in simulation education?

Analytic sample: The 120 staff completing the pre and post simulation surveys, and sample of 80 completing the pre and 6 month surveys. This data is obtained from surveys from the QI project utilizing the required simulation training events.

Analytic approach: Descriptive statistics (mean, proportion) and 95% CIs will be used to summarize staff survey items at each time point, and change from pre-simulation to immediately post-simulation, and pre-simulation to 6 month post-simulation. Plots over time of key survey items will illustrate staff reactions and perceptions over time. Simple paired-data analyses (e.g., paired t-tests, McNemar's test) may be used to test change over time in key items or composites specified a-priori. Where possible, composites of multiple items will be summarized rather than individual items to reduce the number of comparisons and tests made.

Research question 2.2: Does implementation of the simulation protocol decrease morbidity of other individual secondary outcomes (see variables table) during the second stage of labor at Regions Hospital compared to morbidity over the same time period at Methodist Hospital?

Analytic sample: 480 infant/maternal patients (120 Regions before/120 after simulation; 120 Methodist before/120 after simulation). Each sample of 120 is viewed as an independent sample.

Analytic approach: Same as 1.1, but dependent variables for these analyses will include the individual component items of the primary endpoints, and variables listed as “secondary endpoints” in the variable table. Due to the large number of tests conducted, these analyses will be viewed as more exploratory.

Research question 2.4: Is duration of second stage related to maternal and perinatal complications?

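### Research question 2.1 estimates the 6-month change in staff confidence from 6-month responders only, leaves the other staff's earlier scores unused, and gives two different expected 6-month numbers (80 and 96)

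*Combined protocol and SAP*

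**What the plan says.** Section 4 b) ii (Sample size) expects every one of the 120 staff to complete the first two surveys, because these are given at the simulation event. For the third, sent by e-mail, it says: "The response rate for the 6 month survey is expected to be 80%, yielding 96 surveys for this time period". Section 4 g) (Power analysis) also uses 96 for the 6-month comparisons and gives a detectable change of 0.32 SD, against 0.26 SD for the 120 with pre and post surveys.

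Section 4 f), Research question 2.1, gives a different 6-month number: a "sample of 80 completing the pre and 6 month surveys". Its approach is that "Descriptive statistics (mean, proportion) and 95% CIs will be used to summarize staff survey items at each time point". Change is also summarised from pre to immediate post and from pre to 6 months, and key items are plotted over time. Paired t-tests or McNemar's test "may be used to test change over time in key items or composites specified a-priori".

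On missing data, section 4 f) says only that it will be examined with the other descriptives. No section gives a method for 6-month non-response, a comparison of responders with non-responders, or a sensitivity analysis. Survey non-response is not among the limitations in section 4 h).

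**The concern.** A change from pre to 6 months computed in people with both surveys describes those who chose to answer. It describes all trained staff only if non-responders changed, on average, as much as responders did. The time-point summaries and plots add a second problem: the first two points represent 120 people and the third a subset, so a shift in who answers can look like a shift in confidence.

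The 6-month wave is the study's only information on whether any gain lasts. Each non-responder is expected to have two earlier scores, and the immediate-post score is a natural predictor of the 6-month score. The plan makes no use of it for this purpose.

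**Working it through.** **1. Expected 6-month number.** With n=96, 24 of 120 are missing (20%). With n=80, 40 of 120 are missing (33%). The 80 may be the 80% response rate carried over as a count, but the documents do not say.

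**2. The plan's detectable changes.** I took a paired t-test with effect in SD of the change. Power of 80% and two-sided alpha of 0.05 are stated for the maternal composite, and I assume they apply to the survey too. The normal approximation is d = (1.960 + 0.842)/√n; the exact value solves the noncentral t.

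| n | Normal approx. | Noncentral t | Stated |
|---|---|---|---|
| 120 | 0.256 | 0.258 | 0.26 |
| 96 | 0.286 | 0.289 | 0.32 |
| 80 | 0.313 | 0.317 | none |

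The figure for 120 reproduces. The 0.32 attached to n=96 does not; it matches n=80. At n=96, power for 0.32 SD is 87.4%.

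**3. Bias of the responder-only change.** Bias = missing share × (mean change in responders − mean change in non-responders). The gap is not in the documents, so a range is assumed, in SD of the change:

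| Gap | 20% missing | 33% missing |
|---|---|---|
| 0.25 | 0.05 | 0.08 |
| 0.50 | 0.10 | 0.17 |
| 1.00 | 0.20 | 0.33 |

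For a true change of zero to look significant, the bias must reach the confidence-interval half-width: 0.203 at n=96 and 0.223 at n=80. The gap needed is 0.203/0.20 = about 1.0 SD, or 0.223/0.333 = 0.67 SD.

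**4. Simulation.** Assumed: normal scores with unit SD and means 0, 0.8 and 0.5 (pre, post, 6 months); correlations (pre-post, post-6m, pre-6m) of (0.5, 0.7, 0.4) or (0.4, 0.6, 0.4); response odds multiplied by 2 or 3 per SD of the post score or of the immediate gain. Bias is in SD of the score:

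| Estimate | 80% respond | 67% respond |
|---|---|---|
| Paired change, responders only | 0.02 to 0.15 | 0.04 to 0.24 |
| Difference of time-point means | 0.02 to 0.13 | 0.04 to 0.21 |
| Estimate using all 120 pre and post scores | within 0.01 | within 0.01 |

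The standard error of the all-data estimate was equal to or smaller than that of the paired change. With pre-6m correlation 0.4, the SD of the change is √(2 − 2×0.4) = 1.095 score SDs, so 0.15 here is 0.15/1.095 = 0.14 on the scale of step 2.

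Some patterns give no bias. If all correlations are equal and response depends only on the post score, the paired change is unbiased, while the time-point means are still off by 0.06 to 0.09 SD at 80% response. If, with equal correlations, response depends only on the gain, the time-point means are unbiased instead.

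**5. Limits of the model.** When response depends on 6-month confidence itself, the paired bias is 0.06 to 0.12 SD and the all-data bias 0.07 to 0.13 SD (response about 80%; the two correlation sets above plus all correlations 0.5). The model does not help there. The covariance also matters: where response depends on the post score and the paired bias is 0.03 to 0.04 SD, a random-intercept model still leaves 0.02 to 0.04 SD.

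**6. Precision.** Variance is SD² × [R²/120 + (1 − R²)/n], where R² is how well the two earlier scores predict the 6-month change (not in the documents). As R² goes from 1 to 0, the detectable change runs from 0.26 to 0.29 SD with 96 responders and from 0.26 to 0.32 SD with 80. The model's main value is against bias, not for power.

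**The case against.** The strongest reply is that little depends on this. The question asks whether confidence rises after the training, and the pre-to-post contrast, with full response expected, answers that. The paired tests are optional and secondary inference is labelled exploratory. The planned change is within person, so a different starting level alone does not bias it. All of this stands and sets the priority.

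Four stronger readings are tempting, and the documents do not support them.

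- **Non-response inflates the retained gain.** Nothing shows that staff who gained least, or who left, are the ones who fail to answer. Section 5 calls the staff a relatively stable population.
- **Non-responders also drop out of the pre-post comparison**, because the staff criterion requires that they trained "and completed the surveys as part of the QI simulation project". Research question 2.1 defines a separate sample of 120 for pre and post, and sections 4 b) ii and 4 g) keep that number.
- **The surveys cannot be linked by person.** Section 4 d) says only this: "Surveys include a label to identify whether they are gathered before or after the simulation". The survey appendices are not in the text available here, and planned paired tests presuppose linkage. Silence about an identifier does not show that there is none.
- **A repeated-measures model cures the problem.** It does so only if non-response depends on observed scores (step 5).

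**Conclusion.** The point holds as a low-priority improvement. The 6-month change is a responders-only estimate, the plots mix different groups of staff, and nothing in the plan uses the earlier scores of those who do not answer. If response is related to those scores or gains, the bias in the paired change is about 0.02 to 0.15 score SDs at 80% response and 0.04 to 0.24 at 67%, under the response patterns assumed in step 4; in other patterns it is near zero. Bias of this size can blur how much confidence was kept. It is unlikely to create a gain from nothing, which would need responders and non-responders to differ by about 1.0 SD (n=96) or 0.67 SD (n=80).

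The conflict between 80 and 96, and the detectable change that fits only 80, follows from the documents, given the assumed power and alpha. The two primary composites are not affected.

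**What to change.** In section 4 f), Research question 2.1:

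- Estimate both changes, with 95% CIs, from one likelihood-based repeated-measures model with time as a three-level factor (pre, post, 6 months) and an unstructured covariance, including all staff with a pre survey. Use a logistic counterpart for binary items.
- State that the model assumes missing at random given the earlier scores. Add a simple sensitivity analysis in which non-responders have a worse 6-month change, for example by 0.25, 0.5 and 1.0 SD.
- Plot model means, or the same responders at all three times.
- Tabulate pre and immediate-post scores of 6-month responders and non-responders.
- Give one expected 6-month number in sections 4 b) ii, 4 f) and 4 g), and a detectable change that matches it (0.29 SD for 96, 0.32 SD for 80).
- Confirm that the existing surveys are linked by person. If they are not, neither the paired analyses nor this model can be run as described: withdraw the paired analyses and report the time points unpaired.

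The surveys were scheduled for late 2017 and June 2018 and the document is dated July 2019, so the fix is confined to analysis and wording. It costs a few lines of SAP text, slightly more analysis work and a model assumption to state.

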Cesarean delivery during the second stage of labor has been shown to result in a significant increase in maternal and perinatal complications, most often due to difficult delivery of the impacted fetal head [1,2,3,4]. The number of second stage cesarean deliveries is projected to increase for several reasons, particularly due to the overall decrease in operative vaginal deliveries and proposed lengthening of the permissible duration of the second stage of labor [3]. There have been few prospective studies that have compared the two traditional methods of delivery of an impacted fetal head, elevating the fetal head through the vagina (push method) or reverse breech extraction (pull method). These studies have suggested that the pull method is associated with fewer complications [3, 4, 5, 6]; however, there is no definitive, evidence based algorithm to guide management of these difficult deliveries. Because extraction of the fetal head during second stage deliveries can be an obstetric emergency, it necessitates team and provider education to facilitate anticipation, communication and timely management by all team members. Team simulations for obstetric emergencies have been shown to assist with provider comfort, improved clarity of thinking, and quicker action during emergency situations resulting in improved outcomes. Our study aims to show that simulation education for the entire obstetric team can decrease morbidity of difficult fetal head extraction associated with second stage cesarean deliveries and improve provider and nursing staff confidence regarding anticipation and management of this emergency.

QI Project Description:

The simulation education project is not being conducted primarily for the purpose of research, but is a department-wide educational activity and QI project that will be required for all OB staff physicians, residents, nursing staff, and surgical techs at Regions hospital that work in the Birth Center. There are 120 providers or “birth center cesarean section delivery team members” at Regions hospital. Each staff person is required to attend one of the sessions. There will be 6 simulation education events at Regions hospital with approximately 20 individuals attending each two hour session. A pre and post survey will be given at the simulation event. A 3rd survey 6 months after the simulation event will also be distributed to assess team member confidence regarding second stage cesarean sections.

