The timeline of the simulation will be as follows: Pre simulation survey- 10 min, ACOG second stage cesarean section slide presentation- 20 min, practice with mannequins (separate for nursing and physician providers based on skill sets required)- 40 mins, combined second stage cesarean section scenario with whole team with debrief- 40 min, Post simulation survey- 10 min. This simulation will be based on a presentation given at the ACOG meeting in 2016. Simulations will be led by [name], [name], [name], and [name] from mid October 2017 through mid-December 2017 in the simulation center at Regions hospital.

All birth center team members will be notified regarding the simulation events by email and at staff meetings and will be required to attend 1 simulation event from mid-October-December 2017. Three additional simulation events will be offered during the project period for new Birth Center staff.

4. Approach

a. Study design: This study is an observational, time (pre vs. post simulation) by group (Regions vs. Methodist) design using a retrospective programmatic and manual chart review to evaluate the morbidity of second stage cesarean deliveries before and after implementation of

simulation education at Regions Hospital from July 2014 to June 2019. The same morbidity metrics will be gathered from patients at Methodist Hospital during the same pre and post-time periods to serve as a comparison group. Differential pre-post change in morbidity across patients at the two sites will serve as the key comparison. We will also assess staff confidence and change in self-confidence in the management of impacted fetal head using data from pre and post simulation Quality Improvement project surveys.

b. Population

i. Inclusion/Exclusion criteria:

Patient inclusion: The patient study population includes all patients age 18-45 who underwent cesarean section during the second stage of labor (during the time period July 2014-June 2019 at Regions hospital and Methodist hospital). Second stage is defined as the time between complete cervical dilation and delivery of the infant. Exclusion criteria include patients who underwent cesarean section in second stage for malpresentations (i.e., breech and noncephalic presentations), patients who underwent cesarean section prior to 37 weeks gestation, and patients on the exclusion list for research.

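### Research question 2.1 plans no breakdown by role, so its pooled change in confidence cannot show whether physicians and nurses both improved

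*Combined protocol and SAP*

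**What the plan says.** Section 4 f), research question 2.1, asks whether the confidence of Regions providers and teams rises after the simulation. The analytic sample is "The 120 staff completing the pre and post simulation surveys, and sample of 80 completing the pre and 6 month surveys". Each survey item is summarised by a mean or proportion with a 95% CI at each time point and for the change. On tests, "Simple paired-data analyses (e.g., paired t-tests, McNemar's test) may be used to test change over time in key items or composites specified a-priori". Neither role nor training session appears in this analysis.

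Other sections describe how the staff differ and how they are trained:

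- Section 4 b) i gives the mix of staff: "50 physicians and 65 nurses and 5 techs".
- The QI Project Description in section 3 says: "There will be 6 simulation education events at Regions hospital with approximately 20 individuals attending each two hour session".
- Its session timetable has one block by role, "practice with mannequins (separate for nursing and physician providers based on skill sets required)- 40 mins", and one joint block, "combined second stage cesarean section scenario with whole team with debrief- 40 min".
- The general text of section 3 sets the goal of improving the confidence of providers and of nursing staff, naming both groups.

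Section 4 g) states a detectable change of 0.26 SD for n=120, pre to post.

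**The concern.** The training is partly role-specific, and the background names two groups whose confidence should rise, but the analysis yields a single change for the pool. Non-physicians are 70/120 = 58% of that pool, so a gain confined to them can carry the overall result. The reverse matters too: a real gain in one group is diluted by the other. Either way, the survey would not answer the aim as section 3 words it.

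A second feature is that the change is produced in six group events and the post survey is answered at the event. If some sessions worked better than others, change scores within a session are correlated, and the independence behind the 0.26 SD and the CIs comes into question. Whether that matters depends on quantities and intentions that the documents do not give.

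**Working it through.** **Inputs from the documents.** 120 staff = 50 physicians + 65 nurses + 5 technicians (sections 4 b) i and ii); 6 sessions of about 20 (section 3); 0.26 SD at n=120 (section 4 g). Two-sided alpha of 0.05 and 80% power are stated there for the morbidity composite and are assumed to carry over to the survey.

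**1. Reproducing the plan's figure.** For a paired t-test on n independent change scores, the detectable change in SD units of change is approximately (1.960 + 0.842)/√n. For n=120 this is 2.802/10.954 = 0.256; the exact noncentral-t value is 0.258. The stated 0.26 therefore reproduces with 120 independent change scores in one pool.

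**2. What a pooled mean can hide.** Assume, for illustration only, that the 70 non-physicians gain 0.5 SD, the 50 physicians gain 0, and the SD of change within each role is 1.

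- Pooled gain: (70/120) × 0.5 = 0.292 SD.
- Power at 0.292 with n=120: 89%.
- Mixing two means adds variance. The pooled SD is √(1 + (70/120)(50/120)(0.5²)) = 1.030, the standardised gain is 0.292/1.030 = 0.283, and power is 87%.

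The pooled test is thus significant about 88% of the time with no change in physicians. If only the 65 nurses gain 0.5 SD, the pooled gain is (65/120) × 0.5 = 0.271 SD and power is 81% with the extra variance included.

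**3. What each role can support.** Same method, independent staff:

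| Group | n | Detectable change (SD) | 95% CI half-width, t/√n (SD) |
|---|---|---|---|
| All staff | 120 | 0.26 | 0.18 |
| Physicians | 50 | 0.40 | 0.28 |
| Nurses | 65 | 0.35 | 0.25 |
| Technicians | 5 | about 1.7 | 1.24 |

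Physicians and nurses can each be reported usefully. Five technicians can only be described.

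**4. The session question.** The documents give no intraclass correlation (ICC) of change scores within a session; 0 to 0.10 is assumed. Design effect = 1 + (20 − 1) × ICC, and the standard error is multiplied by its square root. The 5-df column uses the t distribution that six session means leave. The last two columns are the true error of the plain paired t-test at nominal 5% (40,000 simulated data sets of 6 × 20). They treat the six sessions either as a random sample of possible sessions or as the only sessions of interest.

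| ICC | Design effect | CI width factor | Detectable change (SD) | Same, 5 df (SD) | Error, sessions random | Error, sessions fixed |
|---|---|---|---|---|---|---|
| 0 | 1.00 | 1.00 | 0.26 | 0.32 | 5% | 5% |
| 0.01 | 1.19 | 1.09 | 0.28 | 0.35 | 7% | 4.9% |
| 0.05 | 1.95 | 1.40 | 0.36 | 0.45 | 16% | 4.5% |
| 0.10 | 2.90 | 1.70 | 0.44 | 0.55 | 25% | 4.0% |

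The plain test errs only when ICC is above zero and the inference reaches beyond these six sessions.

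**The case against.** The research question is worded for providers and the team, and the variables table lists the endpoint as confidence of medical staff. A pooled mean answers that wording. Half of the 80 minutes of hands-on training is joint. The 0.5 SD versus zero split is hypothetical. The aim is secondary, its tests are optional, and section 4 f) calls inference on secondary endpoints exploratory. All of this stands, and it limits how serious the point is. It does not remove the point: section 3 names both groups, and the exploratory label concerns multiple testing, not what a pooled mean can reveal.

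A reader might infer three stronger things that the documents do not support.

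- *That the CIs are too narrow.* This needs sessions that differ in effect and an inference beyond them. No ICC is given, and the format is the same for every session; a feature common to all six shifts the mean without creating variation between sessions. The six events are the whole initial programme, and all 120 staff must attend. With sessions taken as fixed, the plain paired t-test is not anticonservative.
- *That a nurse gain will be presented as a surgeon gain.* Nothing in the plan says a pooled rise will be reported in that way.
- *That role or session is not collected.* The surveys are described as appended, but the appendices are not in the text available, so this cannot be judged.

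**Conclusion.** The point holds for role. As written, research question 2.1 cannot show whether physicians and nurses both gained confidence: a 0.5 SD gain among non-physicians alone would give a pooled 0.29 SD, significant about 88% of the time. That figure rests on an illustrative split and a within-role SD of change of 1. The structural fact, that one mean cannot separate two groups, rests on no assumption.

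The session point is conditional. The 0.26 SD and the CIs are right if the training effect does not vary between sessions, or if the inference is confined to these six. If the result is to be generalised, for example to the three later events for new staff, the design effect runs from 1.0 to 2.9 over the assumed ICC range. That supports a stated assumption and a sensitivity analysis, not a different primary method, since a variance component from six sessions is poorly estimated.

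The primary maternal and infant analyses are untouched.

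**What to change.** 1. For each composite specified in advance, report the pre-to-post and pre-to-6-month change with 95% CI for physicians and for nurses, beside the overall change. Describe the technicians without inference.
2. In section 4 g), add the pre-to-post role-specific detectable changes: about 0.40 SD for 50 physicians and 0.35 SD for 65 nurses. Say that these and the 0.26 SD assume independent change scores.
3. State whether the inference is to these six sessions or to such sessions in general. If the latter, and if session is recorded, add a session-adjusted interval with a small-sample correction (about 5 df) as a sensitivity analysis.

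**Cost.** Role must be in the survey file, and session too for item 3. Intervals widen: the half-width rises from 0.18 SD for all staff to 0.28 SD for physicians and 0.25 SD for nurses. The session-adjusted interval costs precision even when sessions do not differ (detectable change 0.32 SD at ICC 0). With only five technicians, role combined with session could identify individuals, so the file sent to the statistician needs care in view of the de-identification commitment in section 7.

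While editing, reconcile the 6-month sample: 80 under research question 2.1, but 96 in sections 4 b) ii and 4 g). The 0.32 SD attached to n=96 is the value for n=80; n=96 gives 0.29 SD.
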